7.3 Collection of Clinical Data

Study participants will provide consent for study personnel to access their obstetrical record for information about age, fetal sex, potential confounders (see exclusion criteria) and gestational age at sample collection.

8.0 Intervention Modification Based on Adverse Events: Not applicable

9.0 Ancillary Treatment/Supportive Care: Not applicable.

10.0 Adverse Event (AE) Reporting and Monitoring

10.11 Adverse events will be assessed as a routine part of every clinic visit during pregnancy. These will be reported to the principal investigator. The principal investigator will make a decision on whether the adverse event is expected or unexpected, and if the adverse event is related to the procedure. Based on this information, the PI will determine whether the adverse event should be reported as an expedited report or as part of routine clinical data.

There are no known risks of ultrasound imaging to either the mother or fetus during pregnancy. Therefore, we expect no study related adverse events to occur.

10.12 Expected vs. Unexpected

- The determination of whether an AE is expected is based on whether the event is generally associated with the condition being studied (i.e. IUGR), whether in the research study or in the setting of standard clinical care.
- Unexpected AEs are those events that are generally not associated with the condition being studied and may have a relationship to the procedure or device (i.e. ultrasound) being studied.

10.13 Assessment of Attribution

When assessing whether an adverse event is related to a medical treatment or procedure, the following attribution categories are utilized:

- Definite - The adverse event *is clearly related* to the specimen collection.
- Probable - The adverse event *is likely related* to the specimen collection.
- Possible - The adverse event *may be related* to the specimen collection.
- Unlikely - The adverse event *is doubtfully related* to the specimen collection.
- Unrelated - The adverse event is clearly *NOT related* to the specimen collection.

11.0 Intervention Evaluation: Not applicable.**12.0 Descriptive Factors:** None.**13.0 Follow-up Decision at Evaluation of Patient**

- 13.1 Women who have either (a) developed NO pregnancy complications, or (b) developed IUGR will be **eligible** for the research ultrasound and placental pathology review.
- 13.2 Women who have developed pregnancy complications including but not limited to those complications listed below will be **ineligible** if:
 - 13.21 They develop a severe infection
 - 13.22 If they have any other complication which is felt by the study participant's obstetrician to preclude her from further participation in the study
- 13.3 If an eligible participant after signing a consent form refuses to undergo the research collections required, no further data submission is necessary.
- 13.4 When a participant is found to be *ineligible* (that is, the patient is determined not to have satisfied each and every eligibility criteria for study entry at the time of registration), the participant will discontinue further study participation.
- 13.5 A participant may discontinue study participation at any time.

14.0 Human Studies Evaluation

14.1 Vulnerable population

Our protocol is in accord with the Code of Federal Regulations, Part 46: Protection of Human Subjects (section 46.204), which states that pregnant women may be involved in research if the following conditions are met: (1) there is a prospect of direct benefit to pregnant women and their fetuses, (2) the risk to the fetus is not greater than minimal, and (3) the purpose of the research is the development of important biomedical knowledge that cannot be obtained by other means.

Fetuses diagnosed with IUGR and/or preterm labor/birth face a significant risk of morbidity and mortality before their first birthday. Currently, we don't know what causes IUGR or spontaneous preterm birth, but many studies indicate the immune system is a significant contributor to their pathobiology. VUE is strongly associated with these diagnoses and has a significant risk of recurrence in a subsequent pregnancy. New animal data suggests that prenatal ultrasound may be a real-time clinical tool for assessing fetal risk of adverse outcomes. Identifying placental inflammation early may allow for effective intervention to minimize placental damage and therefore improve fetal and neonatal outcomes.

15.0 Statistical Considerations and Methodology

15.1 This is a feasibility study; therefore, no formal power analysis was completed

A total of 61 women will be accrued; 40 with a diagnosis of IUGR and 20 gestational age matched controls (+/- 1 week) will be analyzed. These women must be undergoing obstetric care for their pregnancy at Mayo Clinic. We are not offering remuneration; however, based on our previous studies we had a high recruitment and retention rate.

All statistical analyses will be performed using JMP version 10.0 (SAS Institute). Data will be examined for normality using the Shapiro-Wilk test, and between-group differences in expression for each ultrasound measure in our three groups will be analyzed with the nonparametric Kruskal-Wallis tests (non-parametric) or ANOVA (parametric). Dunn's method will be utilized to correct for multiple comparison testing. P-values <0.05 will be considered statistically significant.

Principal component analysis (PCA) will be used to assess the ability of the biomarker panel to separate individual data points (score plot) by projection of the original data on the first two principal components (PC1 and PC2), as well as correlations among ultrasound measures (loading plot). This will reduce the complexity of multidimensional data models by linearly combining multiple factors and downsizing them into new variables or principal components while retaining the original information.

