1.0 Background

Many pregnancy complications, including growth restriction, preterm birth and stillbirth, are associated with inflammation in the placenta, which is currently diagnosed after delivery. This non-infectious placental inflammation is known as villitis of unknown etiology (VUE) is characterized by maternal T cells infiltrating into the placenta and causing destruction of the villous architecture. However, it's not known what leads to these maternal T cells becoming activated against fetal cells, nor it is understood whether VUE is a cause or an effect of the associated fetal complications. The main challenge faced by researchers studying VUE is that there are no strategies to predict VUE *in utero*.

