1.1 Villitis of Unknown Etiology

Intrauterine growth restriction (IUGR) appears to be associated with a placental pathology called villitis of unknown etiology (VUE).¹ During VUE, maternal T cells are found at high levels in the chorionic villi, causing destruction of placental architecture without clinical signs and symptoms of maternal (or fetal) infection.² VUE is diagnosed in 30% of all placentae.³ However, exact prevalence and the significance of this diagnosis, along with its potential role in IUGR, remains unknown. As half of a fetus' genetic material is paternally derived, VUE may represent a rejection response by the maternal immune system. Human leukocyte antigens (HLA), which are critical to the success of organ transplantation, may provide novel insights into VUE. Our published work identified that HLA class I and II receptors are upregulated in placentae with VUE compared to unaffected, gestational age-matched controls.⁴ Additionally, HLA-typing of VUE affected mothers and their newborns demonstrated increased HLA-mismatch compared to unaffected pairs.⁴ Our follow-up data (in review) utilizing T cell receptor spectratyping shows a significant expansion of T cell clones in placentae with VUE compared to controls; however, these clones are unique to each subject further indicating VUE is not a response to a shared antigen (as with an undetected infection).

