1.2 Ultrasound Imaging

The scientific premise for this project is supported by strong animal data out of John Hopkins. This group utilized *in utero* Doppler ultrasound to identify intrauterine inflammation in a mouse model. Pregnant mice injected with lipopolysaccharide into the uterine cavity have intrauterine inflammation, which researchers found to cause elevated resistance indices, pulsatility indices and a greater occurrence of absent end-diastolic flow in the umbilical and uterine arteries.⁵ Women diagnosed with fetal IUGR during pregnancy will undergo Doppler ultrasound to monitor signs of fetal health. Inflammation is also associated with abnormal growth of microvessels.^{6,7} Current Doppler technology is not sensitive enough to detect these microvessels, whereas the new microvessel imaging technology can detect these small changes in blood flow.^{8,9} Therefore, as microvessel change is associated with inflammation, and inflammation is related to VUE and its associated fetal complications, we believe combining Doppler imaging with microvessel imaging will provide more power to identify placental villitis, possibly even those cases of mild villitis. Additionally, we will measure the ultrasound attenuation coefficient (UAC) in the placenta¹¹, which would provide information on fat fraction that may be a useful evaluation of placenta health.

Study Plan: This study will collect:

1. Ultrasound measures during the third trimester (>28 weeks)
2. Clinical placental specimen after birth
3. Patient demographics from the electronic medical record

Studies utilizing these three things will be performed as described in the sections that follow.

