2.0 Goals

We aim to develop an ultrasound method to identify VUE induced inflammation in the human placenta during gestation. We hypothesize that hemodynamic changes can also be observed in the human placenta diagnosed with VUE by conventional Doppler ultrasound and microvessel imaging (also called 3D imaging in the consent form).

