2.1 Primary

3.11 Our goal is to determine whether Doppler ultrasound measures of blood flow can predict VUE during gestation in a cohort of growth restricted fetuses compared to normal controls.

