7.0 Protocol Intervention

This study will take place in the Rochester Methodist Hospital and will enroll women attending antenatal care through the Department of Obstetrics and Gynecology. Annually, 2500 women receive care and deliver at the Mayo Clinic Family Birth Center. This study will consist of two cohorts: 1) women diagnosed with intrauterine growth restriction (IUGR) and 2) women having uncomplicated pregnancies. Forty women will be enrolled after being diagnosed with IUGR. Based on our clinical data we expect 50% to have a VUE diagnosis. Another cohort of 20 women having uncomplicated pregnancies will be enrolled, matched on gestational age at ultrasound and fetal sex.

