7.1 Study Methodology

Following consent, women will undergo a comprehensive Doppler ultrasound of the placenta. Prenatal ultrasound is routinely used in clinical practice and considered safe. The ultrasound output level used in this study will be below the FDA limit for fetal imaging. Ultrasound measures to be collected include uterine artery (UtA) and

umbilical artery (UA), systolic/diastolic (S/D) ratio, resistance index (RI), pulsatility index (PI) and presence of early diastolic notch will be collected for each subject.

Additionally, we will explore the benefit of novel ultra-sensitive Doppler technology for microvessel imaging of the placenta. This technology can substantially improve small vessel imaging on ultrasound. A Verasonics ultrasound scanner will be used for ultra-sensitive Doppler imaging. We will collect data on vessel density, periphery-to-center vessel density ratio (VDR), microvessel morphology and the ultrasound attenuation coefficient (UAC). Relevant information about the Verasonics scanner can be found in the Device section.

Maternal and fetal demographics will be collected for all study subjects. Statistical differences between variables in our three groups will be determined ANOVA by Kruskal-Wallis tests if normality is not met. Significance will be defined as a p-value ≤ 0.05 .

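### The primary goal is to predict VUE, but section 15.1 plans no accuracy measure and does not name VUE-positive versus VUE-negative within IUGR as the comparison that answers it

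*Combined protocol and SAP*

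**What the plan says.** Section 2.1 sets the primary goal: to "determine whether Doppler ultrasound measures of blood flow can predict VUE during gestation in a cohort of growth restricted fetuses compared to normal controls". Section 2.0 frames the wider purpose: "We aim to develop an ultrasound method to identify VUE induced inflammation in the human placenta during gestation". Section 1.0 gives the motivation: "The main challenge faced by researchers studying VUE is that there are no strategies to predict VUE" before delivery.

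For the analysis, section 15.1 states that "between-group differences in expression for each ultrasound measure in our three groups will be analyzed with the nonparametric Kruskal-Wallis tests", with ANOVA as the parametric alternative, Dunn's method for multiple comparisons and a 0.05 threshold. It adds a principal component analysis with score and loading plots. Section 7.2 says that VUE severity will be correlated with the ultrasound findings, without naming a method.

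The three groups are not defined. They can be inferred from section 7.0, which enrols 40 women with IUGR and 20 controls and says of the IUGR cohort: "Based on our clinical data we expect 50% to have a VUE diagnosis". That gives IUGR with VUE (VUE+), IUGR without VUE (VUE−) and controls.

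**The concern.** Predicting a condition calls for a measure of how well the marker separates women who have it from women who do not. The plan contains none: no AUC, sensitivity, specificity, cut-off or model with VUE as the outcome. Principal component analysis does not use VUE status, so it cannot supply one.

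The second gap is the comparison. On the inferred groups, Dunn's pairs include VUE+ versus VUE− within IUGR, but the plan does not say that this pair bears on VUE. VUE+ versus control mixes VUE with growth restriction, and the omnibus test can be significant because of growth restriction alone. Section 1.2 makes an IUGR effect on these indices plausible: "Women diagnosed with fetal IUGR during pregnancy will undergo Doppler ultrasound to monitor signs of fetal health". A team could therefore follow the plan, find a significant result and report that Doppler predicts VUE, when it has only detected the growth restriction already diagnosed. An AUC added later against controls, or against all women without VUE, would have the same fault.

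A related gap concerns the controls. Section 7.2 has their placentae reviewed too, and no rule says where a control found to have VUE belongs. Section 1.1 says that "VUE is diagnosed in 30% of all placentae", while calling the exact prevalence unknown.

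**Working it through.** **Inputs.** Section 7.0 gives 40 IUGR women, a 50% expected VUE rate and 20 controls. So 40 × 0.50 = 20 VUE+ and 20 VUE−, with a binomial 95% range of 14 to 26 VUE+. The cohorts sum to 40 + 20 = 60 against the 61 accrued in section 15.1, a difference too small to matter here. The plan gives no power, effect size or precision figure to reproduce, so the shifts below are assumptions.

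**No VUE effect, IUGR shift only.** Data are normal with SD 1, 20 women per group, and both IUGR groups are shifted equally from controls. The rule is ANOVA with Bonferroni pairwise t-tests if every group passes Shapiro-Wilk, otherwise Kruskal-Wallis with Bonferroni-adjusted Dunn tests. The plan does not say how Dunn's method applies after ANOVA; this is assumed. There are 10,000 trials per row.

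| IUGR shift (SD) | Omnibus significant | VUE+ v control | VUE+ v VUE− | AUC v control | AUC v all others | AUC within IUGR |
|---|---|---|---|---|---|---|
| 0 | 5.4% | 1.7% | 1.8% | 0.50 | 0.50 | 0.50 |
| 0.5 | 34% | 19% | 1.6% | 0.64 | 0.57 | 0.50 |
| 0.8 | 72% | 52% | 1.7% | 0.71 | 0.61 | 0.50 |
| 1.0 | 90% | 75% | 1.6% | 0.76 | 0.63 | 0.50 |

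Closed-form check: AUC v control = Φ(shift/√2) = 0.638, 0.714 and 0.760. AUC v all others = 0.5 × 0.5 + 0.5 × Φ(shift/√2); at 1.0 SD this is 0.25 + 0.38 = 0.63. With Kruskal-Wallis alone, the omnibus figures are 31%, 70% and 88%. With a 14/26 or 26/14 VUE split they stay at 34–35%, 71–72% and 90%. At smaller shifts of 0.2 and 0.3 SD, the omnibus test is significant in 10% and 16% of trials, and VUE+ versus control in 4% and 7%.

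**Controls with VUE.** At an assumed 30% rate, 20 × 0.30 = 6 controls (95% range 2–10). At 10%, it is 2 (0–5). Suppose VUE shifts the index by 1.0 SD in every woman who has it, there is no IUGR shift, and k such controls stay in the control group. Then AUC v control = ((20 − k)/20) × 0.760 + (k/20) × 0.5:

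- k = 2: 0.684 + 0.050 = 0.73 (simulated 0.735)
- k = 6: 0.532 + 0.150 = 0.68
- k = 10: 0.380 + 0.250 = 0.63

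If VUE has half the effect in controls, the simulated values are 0.75, 0.73 and 0.70. The within-IUGR AUC stays at 0.76.

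**Precision of the added estimates.** The Hanley-McNeil variance is [A(1 − A) + (n₁ − 1)(Q₁ − A²) + (n₂ − 1)(Q₂ − A²)]/(n₁n₂), with Q₁ = A/(2 − A) and Q₂ = 2A²/(1 + A). At A = 0.75, Q₁ = 0.600, Q₂ = 0.643 and A² = 0.5625.

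- 20 v 20: (0.1875 + 0.7125 + 1.5268)/400 = 0.00607, SE 0.078, 95% CI 0.60–0.90.
- 14 v 26: (0.1875 + 0.4875 + 2.0089)/364 = 0.00737, SE 0.086, 95% CI 0.58–0.92.
- Sensitivity of 15/20: exact 95% CI 0.51–0.91.

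Section 7.1 lists three continuous indices (S/D ratio, RI, PI) in two arteries, so six. With no VUE effect, at least one of six AUC intervals excludes 0.5 in 18% (correlation 0.8) to 35% (correlation 0) of trials.

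**The case against.** The strongest reply is that the plan already contains the right contrast. There are only three pairs, one of them isolates VUE, and Dunn's method tests it. Under the rule above it is significant in about 2% of trials when VUE has no effect, and has 73–75% power for a 1.0 SD VUE effect. The hypothesis in section 2.0 and the microvessel goal in section 2.2 concern differences between groups, which these tests address. Section 2.1 itself asks for a comparison with normal controls. The study is declared a feasibility study, the accuracy intervals will be wide, and the size of the problem rests on assumed shifts.

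Much of this is fair. The contrast is not absent, and the planned tests are not invalid. That the within-IUGR pair answers the VUE part of the goal is a reasoned reading rather than the document's wording. The figures are smaller for small IUGR shifts, and with no shift the problem disappears. The placement of controls with VUE does not affect the within-IUGR result.

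What remains is enough. The primary goal says predict, and no planned result measures prediction. Feasibility status explains the missing power calculation, but not the missing estimate of the stated goal. Nothing in the plan prevents a significant omnibus or control comparison from being reported as evidence about VUE.

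**Conclusion.** The concern holds and should be fixed. Followed exactly, the plan gives no figure for how well Doppler predicts VUE and does not say which result bears on that question. The choice of comparison decides the apparent answer: with no VUE effect and an IUGR shift of 0.5 to 1.0 SD, the AUC is 0.64 to 0.76 against controls and 0.57 to 0.63 against all other women, but 0.50 within IUGR.

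Those sizes assume normal data, equal variances, about 20 women per group, the inferred three groups and shifts that the documents do not supply. The direction does not depend on a particular value: any IUGR effect on an index moves the control-based AUC away from 0.5 while the within-IUGR AUC stays at chance.

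**What to change.** In section 15.1:

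1. State that VUE+ versus VUE− within the IUGR cohort is the comparison that answers the VUE part of the primary goal. For each continuous Doppler index, report the AUC with a 95% CI. Section 7.1 also says "presence of early diastolic notch will be collected for each subject"; for this yes/no finding, report sensitivity and specificity with exact 95% CIs. Label all of these as estimation and report every index, not only the best. Naming one lead index in advance is optional.
2. Keep the three-group tests and the control comparisons that section 2.1 asks for, but state that neither the omnibus result nor VUE+ versus control will be read on its own as evidence about VUE.
3. Define the three groups, and report control comparisons with and without controls found to have VUE.

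The cost is a few sentences and a few lines of analysis, with no new participants or measurements. The drawbacks are the wide intervals and the chance that one of several indices looks predictive by luck, which is why the results should be labelled as estimates and reported in full.

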15.2 Inclusion of Women and Minorities

This study will be available to all eligible women regardless of race or ethnic group. Based upon the most recent birth data at Rochester Methodist Hospital, where approximately 2,500 babies are born each year, 5% of mothers categorized themselves as Hispanic/Latina, 5% as Asian, 6% as Black/African American, 83% White, and 2% other. In 2019, 235 diagnoses of IUGR were made in Rochester, making this study highly feasible.

